13.10 Interim Analysis

Although the final analyses will utilize a 5% Type I error rate, we will use a more conservative interim bound of 0.001 for the *P* value for all interim analyses. Freidlin's[92] simulation studies have demonstrated that such a bound trivially impacts both the interim bounds and the final significance level. Interim analyses will be done in concert with the semi-annual Data Safety Monitoring Board (DSMB) reports. These interim analyses will report on the primary endpoint using all patients that have been on study for at least 3 months.

13.11 Inclusion of Women and Minorities

This study will be available to all eligible patients, regardless of race or ethnic origin. There is no information currently available regarding differential effects in subsets defined by race or ethnicity, and there is no reason to expect such differences to exist. Based on prior smoking cessation studies, we expect about 15% of patients will be classified as minorities by race and about 40% of patients will be male.

Racial Categories	Ethnic Categories				Total
	Not Hispanic or Latino		Hispanic or Latino		
	Female	Male	Female	Male	
American Indian/Alaska Native	9	6	0	0	15
Asian	5	2	1	0	8
Native Hawaiian or Other Pacific Islander	5	2	0	0	7
Black or African American	37	25	0	1	63
White	391	262	7	5	665
More Than One Race	15	10	0	0	25
Total	462	307	8	6	783

14.0 CORRELATIVE AND COMPANION STUDIES

There are two substudies within Alliance A211401. Measurement of saliva cotinine levels is a correlative substudy, which is mandatory for all patients registered to A211401. There is one pharmacogenetics companion substudy, which must be offered to all patients enrolled on Alliance A211401 (although patients may opt to not participate). The companion substudy included within Alliance A211401 is:

- Pharmacogenetics of Smoking Cessation Treatment (POST), Alliance A211401-PP1

14.1 Correlative substudy to measure saliva cotinine levels

14.1.1 Background

For patients enrolled on study, saliva samples will be obtained to analyze for cotinine. Salivary cotinine is an evidence-based biochemical method to confirm tobacco use that significantly increases the accurate identification of current smoking. In cancer patients who are asked about tobacco use in person, approximately 30-40% of current smokers misrepresent smoking status (97-98, Khuri et al.). In cancer patients who participate in phone based assessments, recent data demonstrate that 48% of adult smokers (REF) and up to 80% of childhood cancer survivors (REF) misrepresent smoking status. For this study, a cutoff of 15 ng/mL will be used to define biochemically confirmed current smoking (>15) according to recommendations from the Society for Nicotine and Tobacco Research (95).

14.1.2 Hypothesis/objective

This biomarker will be used to increase the accuracy of tobacco assessment as compared with self-reported tobacco use. The hypothesis is that biochemically confirmed tobacco use will increase the magnitude of difference in study outcomes as compared with self-reported tobacco use. This biomarker will be used for the following objectives:

Primary objective: To evaluate the effect of biochemically confirmed tobacco use on study outcomes

Secondary objectives:

To evaluate the accuracy of self-reported tobacco use among study participants

To evaluate if biochemically confirmed tobacco use correlates with a larger magnitude of difference in study outcomes as compared with self-reported tobacco use

To evaluate longitudinal accuracy of self-reporting among study participants at baseline and throughout the study

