13.3 Primary analysis

Surgical complication incidence rates at 24 weeks after surgery will be compared between the intervention vs. control groups using a Fisher's exact test.

Logistic regression models will supplement the univariate analysis, using complication incidence as the dependent variable and will include smoking status at the time of surgery as an independent variable and also adjust for age, gender, FTND, time between randomization and surgery, and presence of adjuvant chemotherapy and/or radiation therapy. A separate logistic model will be created including treatment arm instead of smoking status. We will also explore the collinear relationship between arm and smoking status to see whether they can be included together in the logistic models.

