13.5 Correlative and companion substudy analyses

13.5.1 Correlative substudy analysis (A211401)

Salivary cotinine is an evidence-based biochemical method to confirm tobacco use that significantly increases the accurate identification of current smoking. Data demonstrate that 30-40% of cancer patients who smoke do not accurately report smoking status even using structured assessments (97-98). As a result, quantitative cotinine analyses (96) will be used to increase the accuracy of identifying current smoking, which will in parallel be used to evaluate changes in study outcomes using a more accurate methodology. For this study, a cutoff of 15 ng/mL will be used to define biochemically confirmed current smoking (>15) according to recommendations from the Society for Nicotine and Tobacco Research (95).

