14.1.3 Methodology

Saliva will be collected in patients as described in 6.2 and patients will be identified as current smokers using a salivary cotinine cutoff of >15 ng/mL (95-96) analyzed by [name] at the Medical University of South Carolina. Parallel evaluations of study outcomes, behavior, and genetic linkages will be performed using self-reported tobacco use assessments and biochemically confirmed tobacco use assessments.

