14.2.2 Hypothesis/objective

To evaluate if biochemically confirmation strengthens associations between genetic markers, behaviors, and study outcomes

To evaluate the predictive role of the nicotinic receptor gene cluster (*CHRNA5-CHRNA3-CHRNA4*) and *CYP2A6* genotypes in smoking cessation among lung cancer patients undergoing surgery.

To evaluate the potential moderating effect of these cessation-relevant genotypes on smoking cessation treatment between the intervention and control groups.

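### The cotinine substudy asks whether confirmed smoking shows a larger association than self-report, but its parallel analyses never estimate the difference between the two

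*Combined protocol and SAP*

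**What the plan says.** Section 14.1.2 states a direction: "The hypothesis is that biochemically confirmed tobacco use will increase the magnitude of difference in study outcomes" relative to self-report. It repeats this as a secondary objective: "To evaluate if biochemically confirmed tobacco use correlates with a larger magnitude of difference in study outcomes as compared with self-reported tobacco use". The first aim in 14.2.2 is similar: "To evaluate if biochemically confirmation strengthens associations between genetic markers, behaviors, and study outcomes".

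Two places describe the method. Section 14.1.3 says: "Parallel evaluations of study outcomes, behavior, and genetic linkages will be performed using self-reported tobacco use assessments and biochemically confirmed tobacco use assessments". Section 13.5.1 says of the cotinine analyses: "which will in parallel be used to evaluate changes in study outcomes using a more accurate methodology". Neither gives a contrast between the two sets of results, an interval for that contrast, a test or a criterion.

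Three other passages bear on the point:
- Section 13.3 has a logistic model for complications that "will include smoking status at the time of surgery as an independent variable", without saying which smoking measure is meant.
- Section 14.1.3 classifies current smokers by cotinine above 15 ng/mL alone. Section 13.4 defines point-prevalence abstinence by self-report and cotinine below 15 ng/mL together.
- Section 14.1.1 says that "approximately 30-40% of current smokers misrepresent smoking status" when asked in person. Section 13.4 describes misreporting among smokers in general as very low.

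**The concern.** The aim is about a difference between two associations measured in the same patients. Running the outcome analysis once per smoking definition answers two other questions: is self-reported smoking associated with the outcome, and is cotinine-defined smoking associated with it? Neither asks whether one association is larger than the other.

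With two sets of results and no stated criterion, a reader is left to compare point estimates or to note which one reached significance. Neither reading has a controlled error rate. The substudy could then report that biochemical confirmation strengthens associations with outcomes or genotypes when the gap between the two estimates is within sampling noise.

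**Working it through.** **1. The plan's own figure.** The cotinine comparison has no sizing of its own. The only sizing is in 13.6: 30% v 20%, two-sided 5%, 80% power, Fisher's exact test. Without continuity correction, n per arm = [1.96 × √(2 × 0.25 × 0.75) + 0.842 × √(0.21 + 0.16)]² / 0.10² = (1.200 + 0.512)² / 0.01 ≈ 293.2, so 294. With correction, (293.2/4) × [1 + √(1 + 4/(293.2 × 0.10))]² ≈ 313. Exact Fisher power at 313 per arm is 80.2%. The figure of 626 reproduces and is used below.

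**2. What parallel analyses leave out.** Let b_C and b_S be the cotinine and self-report associations. The aim concerns d = b_C − b_S, with Var(d) = Var(b_C) + Var(b_S) − 2 Cov(b_C, b_S). Two separate model outputs give the two variances but not the covariance. A reader therefore cannot recover the error of d from the planned output.

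**3. How often cotinine gives the larger point estimate.** Simulated trials of 626 patients. Smoking prevalence and classification accuracy are assumptions, because the documents do not give them for this population at surgery.

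| Situation | Assumptions | Cotinine larger |
|---|---|---|
| Equally informative measures | 60% smoking; 20% complications in non-smokers; OR 1.4-3; sensitivity 0.90, specificity 0.98 for both | 49-51% |
| Equally informative measures | 50% smoking; 30% v 20% complications; 10% or 35% of smokers missed by each | 50-51% |
| Smoking unrelated to outcome | 25% complications in all; 30-70% smoking | 43-53% |
| Self-report correct, cotinine adds noise | 50% smoking; 10-35% of non-smokers reclassified | 16-27% |
| Self-report correct, cotinine adds noise | 60% smoking | 21-37% |
| Classifications identical | – | always tied |
| Cotinine better: 35% of smokers deny smoking | 60% smoking; OR 1.4 | 67-73% |
| Cotinine better: 35% of smokers deny smoking | 60% smoking; OR 2 | 82-92% |

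The ranges in the last two rows come from varying the accuracy of cotinine and the specificity of self-report. The value near 50% in the first rows follows from symmetry: when both estimates have the same expected value, either is as likely to be the larger.

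**4. A hand check of the under-reporting case.** Assume 50% smoke at surgery, with complications in 30% of smokers and 20% of non-smokers (the arm rates of 13.6, borrowed). Cotinine is taken as correct and self-report misses a share m of smokers.
- m = 0.30: risk among self-reported non-smokers = (0.50 × 0.20 + 0.15 × 0.30) / 0.65 = 0.2231. The self-report risk difference is 0.30 − 0.2231 = 0.0769, against 0.10 for cotinine, so d = 0.0231. The simulated SD of d is 0.028, so z = 0.82.
- m = 0.40: (0.10 + 0.20 × 0.30) / 0.70 = 0.2286, giving a risk difference of 0.0714 and d = 0.0286. The SD is 0.033, so z = 0.87.

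P(cotinine larger) ≈ Φ(0.82) to Φ(0.87), about 80-81%. P(lower 95% limit above zero) ≈ Φ(0.82 − 1.96) to Φ(0.87 − 1.96), about 13-14%. Direct simulation with a paired bootstrap gave 80-82% and about 14%.

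**5. Effect of a paired interval.** Requiring the lower limit of the paired bootstrap interval to exceed zero cuts false support for cotinine from about 50% to 2.6% (smoking affects complications) or 3.2% (it does not), when the two measures are equally informative. In the 60%-smoking scenarios with 35% misreporting, the interval excludes zero in roughly 6-9% of trials at OR 1.4 and 14-28% at OR 2.

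**6. Why direction must be stated.** In the 60%-smoking noise scenario, an interval excluding zero on either side occurred in 10-17% of trials, nearly always because cotinine was weaker. A rule without direction would count those trials as support.

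**The case against.** The strongest reply is that no passage says the larger estimate, or the significant one, will be taken as the answer. That stands. A reader might infer that the plan decides the question by a coin toss, or that cotinine would win half the time even if it added nothing. The documents support neither. They state no decision rule, and the half applies only when the two measures are equally informative. If cotinine merely adds noise to correct self-report, the share falls to 16-37% across the assumptions tried. Nor does the half arise because the estimates share patients; symmetry gives it, and sharing patients makes the difference more precise. Comparing significance is not a coin toss either: with equal accuracy, cotinine alone was significant in about 11%, 5% and 0% of trials at OR 1.4, 2 and 3.

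A second reply is that the substudy assumes unequal accuracy, since 14.1.1 quotes 30-40% misrepresentation. On that premise the larger estimate usually does point to cotinine. But the premise is what the substudy sets out to test, 13.4 describes misreporting differently, and a correct direction is still not evidence of a difference.

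A third reply is that 13.5.2 puts magnitude ahead of significance for the correlative genetic analyses. This is a fair reason not to impose a significance rule on the genetic aims. It does not replace an estimate of the difference in magnitude with its interval.

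**Conclusion.** The point holds as a low-cost improvement. Sections 14.1.2 and 14.2.2 pose a comparison that the parallel analyses of 14.1.3 and 13.5.1 do not estimate. The size depends on how good the two measures are: cotinine would give the larger point estimate in about half of trials if they are equally informative, in fewer if it only adds noise, and in about 67-92% at OR 1.4-2 if about 35% of smokers under-report. All of these rest on 626 patients with both measures and on assumed prevalence, accuracy and effect size.

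The aim is one secondary objective of a correlative substudy, with a related aim in the genetic substudy. Nothing here touches the primary Fisher comparison or the sample size.

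**What to change.** Add to 14.1.3, covering 14.1.2 and the first aim of 14.2.2:

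- **Definitions.** Name the self-report item and the visit. Use cotinine above 15 ng/mL as in 14.1.3, and state that this differs from the combined abstinence definition in 13.4.
- **Patients.** Fit both definitions in the same patients, namely those with both measures at that visit.
- **Effect measure.** Use that of each outcome's planned model: log odds ratio for complications, mean difference for quality-of-life scores, log hazard ratio for length of stay. A log odds ratio alone would not fit the outcomes in 13.4.
- **Estimate.** Report the difference in association, oriented in advance so that positive means stronger with cotinine, with a 95% confidence interval from a bootstrap that resamples patients and refits both models. Label it exploratory.
- **Criterion.** For complications, say that confirmation strengthens the association only if the lower limit exceeds zero. For the genetic aims, report the difference and its interval descriptively, in keeping with 13.5.2.

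The cost is a paragraph of text and a short computation. Section 6.2 already requires saliva at baseline, surgery and weeks 6, 12, 18 and 24, and the study calendar has the tobacco use assessment at the same visits. The downside is low precision: the interval will often include zero even if the hypothesis is true, so the claim becomes harder to make.

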14.1.3 Methodology

Saliva will be collected in patients as described in 6.2 and patients will be identified as current smokers using a salivary cotinine cutoff of >15 ng/mL (95-96) analyzed by [name] at the Medical University of South Carolina. Parallel evaluations of study outcomes, behavior, and genetic linkages will be performed using self-reported tobacco use assessments and biochemically confirmed tobacco use assessments.

14.2 Pharmacogenetics of Smoking Cessation Treatment (POST), Alliance A211401-PP1

14.2.1 Background

Alliance 211401-PP1 will evaluate genetic effects on cessation outcomes and treatment response. [name] and [name] will identify genetic predictors for cessation outcomes and treatment response. (See section 1.1.4 for more background information).

14.2.2 Hypothesis/objective

To evaluate if biochemically confirmation strengthens associations between genetic markers, behaviors, and study outcomes

To evaluate the predictive role of the nicotinic receptor gene cluster (*CHRNA5-CHRNA3-CHRNA4*) and *CYP2A6* genotypes in smoking cessation among lung cancer patients undergoing surgery.

To evaluate the potential moderating effect of these cessation-relevant genotypes on smoking cessation treatment between the intervention and control groups.

14.2.3 Methodology

Participants will provide a blood sample of 10ml (EDTA Vacutainer) for assessment of genotyping and nicotine metabolism by Washington University. Multiple genes have been shown to predict abstinence and response to cessation pharmacotherapy. The blood sample will be used to extract DNA and the plasma will be used for the biomarker, NMR (ratio of 3'hydroxycotinine/cotinine) which reflect *CYP2A6* activity and nicotine clearance in smokers, and may predict smoking cessation. All blood samples will be collected, stored, and shipped to the Alliance biorepository and will subsequently be shipped to [name] at Washington University in St. Louis for genotyping and nicotine metabolism essays.

15.0 TEACHABLE MOMENT TRAINING

Surgeons and designated members of the surgeon's team will be trained and educated in the basics of smoking cessation counseling and delivery of the No-Smoking message to the surgical oncology patient. The training will be based upon a validated approach to clinician-delivered tobacco use intervention (Warner et al, Anesthesiology 114:847-855, 2011). Two different training modules will be required: One for the surgeon and one for the site staff (study coordinator/nurse). Modules will be on-line and asynchronous, and available on the Alliance Web site via a link on the study-specific web page. Sites will certify that the training was completed by notifying the study chair or co-chair via email. To supplement this training, there will also be a training exercise at the Fall Alliance meeting.

15.1 Surgeons

The module will emphasize the importance of brief surgeon advice to quit and the compelling rationale for smoking cessation to reduce perioperative complications.

The surgeon module will require approximately 5 minutes to complete

15.2 Study Staff

The module will demonstrate the brief behavioral intervention to be delivered by the study coordinator/nurse, including the elements addressed in Section 7.1.

The study staff module will require approximately 30 minutes to complete.

APPENDIX I: SURGICAL COMPLICATIONS ASSOCIATED WITH CIGARETTE SMOKING [104]

30-day mortality 30-day re-hospitalization 1-year mortality Anastomotic failure Anesthesia-related respiratory complications Bleeding (transfusions >5 U) Coma (>24 hours) Deep venous thrombosis/thrombophlebitis Failure to wean from the ventilator ICU readmission Impaired bone healing Implant loss (breast reconstruction)	Increased postoperative pain Renal insufficiency/failure Return to operating room Sepsis/septic shock Stroke/cerebral accident Surgical infection (organ space) Surgical site infections Urinary tract infections Increased postoperative surgical stay Increased scarring and asymmetry Intubation (unplanned)/re-intubation Lower rates of successful digital replantation (microsurgery) Myocardial infarction	Pneumonia Prolonged intubation Prolonged ventilator support Pulmonary complications Pulmonary embolism Reduced skin flap survival Vascular complications Vein graft failure Venous thromboembolism Ventilator (>48 hours) Wound healing (delayed) Wound infection (sternal) Wound infections (superficial and deep)
--	---	---

APPENDIX III: CONTEMPLATION LADDER

Directions: Please complete the following concerning your readiness to quit smoking.

Each number below represents where various tobacco-users are in their thinking about quitting. Circle the number that indicates where you are now.

10	→	I am ready to quit now.
9		
8	→	I have cut down or am seriously thinking of quitting.
7		
6	→	I am thinking about cutting down or quitting.
5		
4	→	I think I should quit but I'm not quite ready.
3		
2	→	I think I need to consider quitting some day.
1		
0	→	I am not ready to quit.

APPENDIX IV: SMOKING SELF EFFICACY QUESTIONNAIRE (SEQ12)

The following are some situations in which certain people might be tempted to smoke.

Directions: Please indicate whether you are sure that you could *refrain* from smoking in each situation by placing an "X" in the appropriate box.

1. When I feel nervous (*check one*)

Not at all sure Not very sure More or less sure Fairly sure Absolutely sure

2. When I feel depressed (*check one*)

Not at all sure Not very sure More or less sure Fairly sure Absolutely sure

3. When I am angry (*check one*)

Not at all sure Not very sure More or less sure Fairly sure Absolutely sure

4. When I feel very anxious (*check one*)

Not at all sure Not very sure More or less sure Fairly sure Absolutely sure

5. When I want to think about a difficult problem (*check one*)

Not at all sure Not very sure More or less sure Fairly sure Absolutely sure

6. When I feel the urge to smoke (*check one*)

Not at all sure Not very sure More or less sure Fairly sure Absolutely sure

7. When having a drink with friends (*check one*)

Not at all sure Not very sure More or less sure Fairly sure Absolutely sure

8. When celebrating something (*check one*)

Not at all sure Not very sure More or less sure Fairly sure Absolutely sure

9. When drinking beer, wine or other spirits (*check one*)

Not at all sure Not very sure More or less sure Fairly sure Absolutely sure

10. When I am with smokers (*check one*)

Not at all sure Not very sure More or less sure Fairly sure Absolutely sure

11. After a meal (*check one*)

Not at all sure Not very sure More or less sure Fairly sure Absolutely
sure

12. When having coffee or tea (*check one*)

Not at all sure Not very sure More or less sure Fairly sure Absolutely
sure

APPENDIX V: FAGERSTRÖM TEST FOR NICOTINE DEPENDENCE

Directions: Please read each question below.

Check only one box for each question that best describes your response.

1. How soon after you wake up do you smoke your first cigarette? (check one)

- Within 5 minutes
- 6-30 minutes
- 31-60 minutes
- After 60 minutes

2. Do you find it difficult to refrain from smoking in places where it is forbidden, e.g. in church, at the library, in cinema, etc.? (check one)

- Yes
- No

3. Which cigarette would you hate most to give up? (check one)

- The first one in the morning
- Any other

4. How many cigarettes per day do you smoke? (check one)

- 10 or less
- 11-20
- 21-30
- 31 or more

5. Do you smoke more frequently during the first hours after awakening than during the rest of the day? (check one)

- Yes
- No

6. Do you smoke even when you are so ill that you are in bed most of the day? (check one)

- Yes
- No

APPENDIX VI: PATIENT HEALTH QUESTIONNAIRE – 9 (PHQ-9)

Over the last 2 weeks, how often have you been bothered by any of the following problems?

1. Little interest or pleasure in doing things

- 0 – Not at all
- 1- Several days
- 2 – More than half the days
- 3- Nearly every day

2. Feeling down, depressed, or hopeless

- 0 – Not at all
- 1- Several days
- 2 – More than half the days
- 3- Nearly every day

3. Trouble falling or staying asleep, or sleeping too much

- 0 – Not at all
- 1- Several days
- 2 – More than half the days
- 3- Nearly every day

4. Feeling tired or having little energy

- 0 – Not at all
- 1- Several days
- 2 – More than half the days
- 3- Nearly every day

5. Poor appetite or overeating

- 0 – Not at all
- 1- Several days
- 2 – More than half the days
- 3- Nearly every day

6. Feeling bad about yourself – or that you are a failure or have let yourself or your family down

- 0 – Not at all
- 1- Several days
- 2 – More than half the days
- 3- Nearly every day

7. Trouble concentrating on things, such as reading the newspaper or watching television

- 0 – Not at all
- 1- Several days
- 2 – More than half the days
- 3- Nearly every day

8. Moving or speaking so slowly that other people could have noticed? Or the opposite – being so fidgety or restless that you have been moving around a lot more than usual.

- 0 – Not at all
- 1- Several days
- 2 – More than half the days
- 3- Nearly every day

9. Thoughts that you would be better off dead or of hurting yourself in some way

- 0 – Not at all
- 1- Several days
- 2 – More than half the days
- 3- Nearly every day

For office coding _____ + _____ + _____ + _____

= _____

If you checked off any problems, how difficult have these problems made it for you to do your work, take care of things at home, or get along with other people? (check one)

- Not difficult at all Somewhat difficult Very difficult Extremely difficult

